### 5.4.3. Treatment of Infusion Related Reactions

Acute infusion reactions (which can include cytokine release syndrome, angioedema, or anaphylaxis) are different from allergic/hypersensitive reactions, although some of the manifestations are common to both AEs. Signs and symptoms usually develop during or shortly

after drug infusion and generally resolve completely within 24 hours of completion of infusion. Signs/symptoms may include: allergic reaction/hypersensitivity (including drug fever); arthralgia (joint pain); bronchospasm; cough; dizziness; dyspnea (shortness of breath); fatigue (asthenia, lethargy, malaise); headache; hypertension; hypotension; myalgia (muscle pain); nausea; pruritus/itching; rash/desquamation; rigors/chills; sweating (diaphoresis); tachycardia; tumor pain (onset or exacerbation of tumor pain due to treatment); urticaria (hives, welts, wheals); vomiting.

For an individual subjects, once the AGEN2034 infusion rate has been decreased by 50% or interrupted due to an infusion-related reaction, it must remain decreased for all subsequent infusions to that subject. If the subject has a second infusion-related reaction that is Grade  $\geq 2$  on the slower infusion rate, infusion should be stopped and the subject should discontinue treatment. If a subject experiences a Grade 3 or Grade 4 infusion-related reaction at any time, the subject must discontinue treatment. If an infusion reaction occurs, all details about drug preparation and infusion must be recorded.

Should infusion reaction be considered a significant safety issue by the SMC, the SMC might decide to recommend premedication with an antihistamine and acetaminophen approximately 30 to 60 minutes before each dose of AGEN2034 (e.g., 25–50 mg diphenhydramine, 500–650 mg paracetamol IV or oral equivalent acetaminophen). This regimen may be modified based on local treatment standards and guidelines, as appropriate.

[Table 3](#) shows treatment guidelines for subjects who experience an infusion reaction associated with administration of AGEN2034.

Subjects receiving AGEN2034 should be monitored for infusion reactions. This includes the measurement of vital signs for at least 1 hour after infusion. Subjects will remain in the clinic under close supervision for the duration of this monitoring period. Subjects with mild or moderate infusion reactions may receive AGEN2034 with close monitoring. Premedication with an antipyretic or antihistamine for subsequent treatment administration may be considered. For severe infusion reactions, AGEN2034 infusion must be discontinued, and appropriate medical therapy should be administered.

Subjects who do not experience any infusion related toxicity Grade 1 or higher during or after the infusion may be released from monitoring after one hour if they are otherwise stable.

Subjects with any infusion related toxicity must be managed as per the guidelines in [Table 3](#) and monitoring will continue until any infusion related toxicity has abated to less than Grade 1 and at least one hour has passed from the completion of the entire infusion and flush. All subjects will be given information on and instructions regarding both infusion related toxicity, which is expected to be most likely in the hour after completion of the infusion, and immune related AEs, before leaving the study site. This will include instructions on when and how to return for immune mediated toxicities associated with PD-1 blockade.

Once the AGEN2034 infusion rate has been decreased by 50% or interrupted due to an infusion-related reaction, it must remain decreased for all subsequent infusions. If the subject has a second infusion-related reaction that is Grade  $\geq 2$  on the slower infusion rate, infusion should be stopped and the subject should discontinue treatment. If a subject experiences a Grade 3 or Grade 4 infusion-related reaction at any time, the subject must discontinue treatment. If an infusion reaction occurs, all details about drug preparation and infusion must be recorded.

Should infusion reaction be considered a significant safety issue by the SMC, the SMC might decide to recommend premedication with an antihistamine and acetaminophen approximately 30 to 60 minutes before each dose of AGEN2034 (e.g., 25-50 mg diphenhydramine, 500-650 mg paracetamol IV or oral equivalent acetaminophen). This regimen may be modified based on local treatment standards and guidelines, as appropriate.

**Table 3: AGEN2034 Infusion Related Reaction Management Guidelines**

CTCAE Grade	Treatment	Premedication at Subsequent Dose
Grade 1: Mild reaction; infusion interruption not indicated; intervention	Increase monitoring of vital signs as medically indicated until the subject is deemed medically stable in the opinion of the investigator.	None.
Grade 2: Requires infusion interruption but responds promptly to symptomatic treatment (e.g., antihistamines, nonsteroidal anti-inflammatories [NSAIDS], narcotics, IV fluids); prophylactic medications indicated for $\leq$ 24 hours.	
Stop infusion and monitor symptoms. Additional appropriate medical therapy may include but is not limited to the following:
 
 
• IV fluids
 
• Antihistamines
 
• NSAIDS
 
• Acetaminophen
 
• Narcotics
 
 
Increase monitoring of vital signs as medically indicated until the subject is deemed medically stable in the opinion of the investigator.
 
If symptoms resolve within 1 hour of stopping drug infusion, the infusion may be restarted at 50% of the original infusion rate. Otherwise, dose administration will be held until symptoms resolve, and the subject should be premedicated for the next scheduled dose.
 
Subjects who develop Grade 2 toxicity despite adequate premedication should be permanently discontinued from further
	
Subject may be pre-medicated 1.5 hours (<math>\pm</math> 30 minutes) prior to infusion with the following:
 
 
• Diphenhydramine 50 mg PO (or equivalent dose of antihistamine).
 
• Acetaminophen 500-1000 mg PO (or equivalent dose of antipyretic).
 

Grades 3 or 4  Grade 3: Prolonged (i.e., not rapidly responsive to symptomatic medication and/or brief interruption of infusion); recurrence of symptoms following initial improvement; hospitalization indicated for other clinical sequelae (e.g., renal impairment, pulmonary infiltrates).  Grade 4: Life-threatening; pressor or ventilatory support indicated.	
Stop infusion.
 
Additional appropriate medical therapy may include but is not limited to:
 
 
• IV fluids
 
• Antihistamines
 
• NSAIDS
 
• Acetaminophen
 
• Narcotics
 
• Oxygen
 
• Pressors
 
• Corticosteroids
 
• Epinephrine
 
 
Increase monitoring of vital signs as medically indicated until the subject is deemed medically stable in the opinion of the investigator.
 
Hospitalization may be indicated.
 
Subject is permanently discontinued from further study drug administration.
	No subsequent dosing.

## 5.4.4. Dose Modifications and Treatment Delay

### 5.4.4.1. Dose Reductions

**No AGNE2034 dose reduction or escalation is allowed.** Each subject will stay on the dose levels assigned in the trial unless treatment needs to be stopped.

### 5.4.4.2. Treatment Delay

#### 5.4.4.2.1. *Criteria for Treatment Delay*

AGEN2034 administration should be delayed for the following:

- Any Grade  $\geq 2$  non-skin, drug-related AE with the following exceptions:
  - Do not delay treatment for Grade  $\geq 2$  Fatigue and laboratory abnormalities except for:
    - Delay dosing for Grade  $\geq 2$  serum creatinine (more than 1.5x baseline) toxicity
    - If a subject has a baseline AST, ALT, or total bilirubin that is within normal limits, delay dosing for drug-related Grade  $\geq 2$  toxicity;
- Any Grade  $\geq 3$  skin drug-related AE or suspected Stevens-Johnson syndrome (SJS) or toxic epidermal necrolysis (TEN)
- Any Grade  $\geq 3$  drug-related laboratory abnormality with the following exceptions for lymphopenia, AST, ALT, or total bilirubin:
  - Grade 3 lymphopenia does not require a dose delay.
  - If a subject has a baseline AST, ALT, or total bilirubin that is within normal limits, delay dosing for drug-related Grade  $\geq 2$  toxicity.
  - If a subject has baseline AST, ALT, or total bilirubin within the Grade 1 toxicity range, delay dosing for drug-related Grade  $\geq 3$  toxicity.
- Any AE, laboratory abnormality, or inter-current illness which, in the judgment of the investigator, warrants delaying the dose of study drug.

Subjects receiving AGEN2034 who have drug-related toxicities that meet the criteria for dose delay should have treatment delayed until retreatment criteria are met.

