- Any Grade 3 drug-related bronchospasm, hypersensitivity reaction, or infusion-related reaction, regardless of duration; with the exception of Grade 3 infusion-related reactions resolving within 6 hours and controlled with medical management;
- Any Grade 3 non-skin, drug-related AE lasting  $>$  7 days, with the following exceptions for uveitis, pneumonitis, bronchospasm, diarrhea, colitis, neurologic toxicity, hypersensitivity reactions, infusion reactions, endocrinopathies, and laboratory abnormalities:
  - Grade 3 drug-related uveitis, pneumonitis, bronchospasm, diarrhea, colitis, neurologic toxicity, hypersensitivity reaction, or infusion reaction of any duration requires discontinuation;
  - Grade 3 drug-related endocrinopathies adequately controlled with only physiologic hormone replacement do not require discontinuation;
  - Grade 3 drug-related laboratory abnormalities do not require treatment discontinuation except:
    - Grade 3 drug-related thrombocytopenia  $>$  7 days or associated with bleeding requires discontinuation;
    - Any drug-related liver function test (LFT) abnormality that meets the following criteria require discontinuation (also see hepatic immune-related AE management algorithm [[Table 7](#)]):

- ▶ AST or ALT  $> 8 \times$  ULN;
- ▶ Total bilirubin  $> 5 \times$  ULN;
- ▶ Concurrent AST or ALT  $> 3 \times$  ULN AND total bilirubin  $> 2 \times$  ULN;
- Any Grade 4 drug-related AE or laboratory abnormality, except for the following events, which do not require discontinuation:
  - Grade 4 neutropenia  $< 7$  days;
  - Grade 4 lymphopenia or leukopenia;
  - Isolated Grade 4 electrolyte imbalances/abnormalities that are not associated with clinical sequelae and are corrected with supplementation/appropriate management within 72 hours after their onset;
- Any AE, laboratory abnormality, or intercurrent illness which, in the judgment of the Investigator, presents a substantial clinical risk to the subject with continued treatment;
- Tumor flare phenomenon, defined as local pain, irritation, or rash localized at sites of known or suspected tumor does not require treatment discontinuation.
- Any requirement for  $\geq 10$  mg per day of prednisone (or equivalent) for  $> 6$  weeks;
- Any recurrence of a Grade 3 or 4 drug-related toxicity;
- Dose delay which results in no AGEN2034 dosing for more than 6 weeks.

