#### 5.4.4.2.2. *Criteria to Resume Treatment*

Subjects may resume treatment with AGEN2034 when drug-related AE(s) resolve(s) to Grade 1 or baseline value, with the following exceptions:

- Subjects may resume treatment in the presence of Grade 2 fatigue.
- Subjects who have not experienced a Grade 3 drug-related skin AE may resume treatment in the presence of Grade 2 skin toxicity.

- Subjects with baseline Grade 1 AST/ALT or total bilirubin who require dose delays for reasons other than a 2-Grade shift in AST/ALT or total bilirubin may resume treatment in the presence of Grade 2 AST/ALT or total bilirubin.
  - Subjects with combined Grade 2 AST/ALT AND total bilirubin values meeting discontinuation parameters ([Section 4.4.1](#)) should have treatment permanently discontinued.
- Drug-related pulmonary toxicity, diarrhea, or colitis must have resolved to baseline before treatment is resumed.
- Drug-related endocrinopathies adequately controlled with only physiologic hormone replacement may resume treatment.
- Subjects who received systemic corticosteroids for management of any drug-related toxicity must be off corticosteroids or have tapered down to an equivalent dose of prednisone  $\leq$  10 mg/day.

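### Confirmed Stevens-Johnson syndrome below Grade 4 triggers no stopping rule, and a resolved Grade 3 case can meet the written criteria to resume AGEN2034

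*Protocol*

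**What the plan says.** - **Delay (Protocol 5.4.4.2.1).** The list of reasons to hold drug includes a Grade 3 or higher "skin drug-related AE or suspected Stevens-Johnson syndrome (SJS) or toxic epidermal necrolysis (TEN". Subjects who meet a delay criterion "should have treatment delayed until retreatment criteria are met".
- **Resumption (5.4.4.2.2).** "Subjects may resume treatment with AGEN2034 when drug-related AE(s) resolve(s) to Grade 1 or baseline value", with listed exceptions. Subjects given systemic steroids for the toxicity "must be off corticosteroids or have tapered down to an equivalent dose of prednisone" of 10 mg/day or less. SJS and TEN are not mentioned.
- **Withdrawal (4.4.1).** The Grade 3 duration rule reads "Any Grade 3 non-skin, drug-related AE lasting" more than 7 days. A second rule names the events that stop drug whatever their duration: "Grade 3 drug-related uveitis, pneumonitis, bronchospasm, diarrhea, colitis, neurologic toxicity, hypersensitivity reaction, or infusion reaction of any duration requires discontinuation". Grade 4 drug-related events also stop drug, with exceptions that include no skin event. Among the general stops are "Dose delay which results in no AGEN2034 dosing for more than 6 weeks" and a need for 10 or more "mg per day of prednisone (or equivalent) for" more than 6 weeks.
- **Table 4, Grade 3-4 row.** Drug is held or stopped as the protocol directs, with a dermatology consult and 1-2 mg/kg/day methylprednisolone. At Grade 1, steroids are tapered over at least a month and drug resumes as the protocol directs.

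**The concern.** The authors singled out suspected SJS/TEN from other skin events, yet the only stated consequence is a hold that ends when general criteria are met. Nothing separates a case that was confirmed from one that was ruled out. Table 4 allows either delay or discontinuation but refers the choice back to the protocol, and no protocol rule settles it by diagnosis.

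The stake is re-exposure of a subject who has had a severe skin reaction to the drug. Section 5.4.4.1 allows no dose reduction, so any re-exposure is at full dose, and treatment may run for up to 24 months. The protocol takes nivolumab as the best guide to AGEN2034 safety (1.1.2.2, 2.2), and Section 1.1.3.2 names TEN among the severe nivolumab events. Its remark there about recurrence after restarting concerns immune-mediated events in general, not TEN in particular. Grade 3 uveitis, pneumonitis and colitis stop drug at any duration; no reason is given for a weaker rule after confirmed SJS.

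**Working it through.** There is no planned figure to reproduce. Two questions decide the point.

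**1. Does any written rule stop drug because of the diagnosis, below Grade 4?**

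| Place | Effect on a confirmed Grade 3 case |
|---|---|
| 5.4.4.2.1 | Hold only |
| 5.4.4.2.2 | Resumption allowed at Grade 1 or baseline. The one skin exception concerns resuming at Grade 2; a prior Grade 3 skin event removes that option but does not bar resumption at Grade 1 |
| 4.4.1, Grade 3 duration rule | Does not apply: non-skin events only |
| 4.4.1, any-duration list | SJS/TEN not named. It would apply only if the event were classed as a hypersensitivity reaction, a link the protocol does not make |
| 4.4.1, Grade 4 rule | Does not reach Grade 3 |
| 4.4.1, general rules | Act on non-resolution within 6 weeks, dosing gap, steroid duration, recurrence or judgment, not on diagnosis |
| Table 4 | Refers back to the protocol for both stopping and resuming |
| 3.1.1, dose-limiting toxicity | Forces withdrawal, but only for Phase 1 escalation subjects in their first 3 weeks, and exempts Grade 3 skin toxicity that falls to Grade 1 or less in under 7 days. Phase 1 enrollment was complete at this amendment (Section 1) |

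The answer is no.

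**2. Can a Grade 3 case resume without meeting a time-based stop?**

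Inputs from the documents:
- The dosing gap may not exceed 6 weeks, or 42 days from the last dose (4.4.1).
- The taper lasts at least 1 month, taken as 30 days, and starts at Grade 1 (Table 4).
- The starting dose is 1-2 mg/kg/day methylprednisolone (Table 4).
- Resumption is allowed at 10 mg/day prednisone equivalent or less (5.4.4.2.2).

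Assumptions not in the documents: body weight 50-80 kg, 1.25 mg prednisone per mg methylprednisolone, and a straight-line taper.

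*Full taper before resuming.* Latest day to reach Grade 1 = 42 - 30 = **day 12** after the last dose.

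*Resuming mid-taper at 10 mg/day.*
- Starting dose in prednisone equivalent: 50 × 1 × 1.25 = 62.5 mg/day, up to 80 × 2 × 1.25 = 200 mg/day.
- Days of taper to reach 10 mg/day = 30 × (1 - 10/start). This gives 30 × (1 - 10/62.5) = 25.2 and 30 × (1 - 10/200) = 28.5.
- Latest day to reach Grade 1: 42 - 25.2 = **day 16.8**, and 42 - 28.5 = **day 13.5**.

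*No systemic steroid.* Only the gap limit binds: **day 42**. This departs from Table 4, which Section 5.6 presents as an aid to investigators.

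The other time-based rules do not close these paths. Steroids started after the last dose cannot have run for more than 42 days by day 42, so the steroid-duration rule is not met. If reaching Grade 1 counts as resolving, as the resumption criterion words it, the 6-week resolution rule is not met either. The recurrence rule acts only on a later event.

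**The case against.** The strongest reply is that withdrawal already reaches the case. Section 4.4.1 requires it once the investigator judges continued treatment a substantial clinical risk, and Section 5.4.4.2.2 permits resumption without requiring it. The first bullet of 4.4.1 also lets the investigator or sponsor stop drug for a safety-relevant event that would have been an exclusion criterion. Suspected immune-related events go to the sponsor within 24 hours, and the safety committee and the data monitoring committee review safety. A hold is also the right first response to a mere suspicion.

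All of that is correct, and it lowers the chance of re-dosing. But each of these routes is discretionary or is oversight. None is triggered by the diagnosis, while the written resumption criteria point towards dosing. A hold suits a suspicion; what is missing is the step after confirmation.

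The path is also narrow. If Table 4 is followed, a Grade 3 event must begin and fall to Grade 1 within about 12 to 17 days of the last dose. The upper part of that range rests on assumptions, and the documents do not reproduce the CTCAE grading of SJS. This stands as a limit on size. The requirement in 6.4.1.11 for a documented investigator-sponsor decision when a toxicity delay exceeds 6 weeks can be read as compatible with withdrawal under 4.4.1, and the conclusion does not depend on it.

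A last objection also stands: Table 4 requires the dermatology consult only at Grade 3-4, whereas the hold applies to suspected SJS/TEN of any grade. The fix has to cover that.

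**Conclusion.** The concern holds. SJS is named once in the two documents, in the delay list. No rule makes a confirmed diagnosis below Grade 4 a reason to stop, and a resolved Grade 3 case can satisfy every written criterion to resume. Grade 4 cases are covered.

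The window is narrow and the potential harm severe. Grade 1 is needed by day 12 with a full 30-day taper, by day 13.5 to 16.8 with mid-taper resumption, or by day 42 without steroids. The mid-taper range rests on the assumed weights, steroid conversion and linear taper. The scenario also assumes that a case can be graded 3 and later 1. No event rate is available, and none is estimated. The response-rate analysis, sample size and error rates are unaffected. This is a safety rule that should be corrected because the remedy is simple and the outcome may be irreversible.

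**What to change.** - **4.4.1:** add that confirmed SJS or TEN, at any grade, requires permanent discontinuation.
- **5.4.4.2.2:** add that after a hold for suspected SJS/TEN, drug may resume only if the diagnosis has been ruled out, on the basis of a dermatology consult whatever the grade. The hepatic bullet in this section already refers to the 4.4.1 discontinuation criteria in the same way.
- **Table 4:** cross-reference the new 4.4.1 entry in the Grade 3-4 row.

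The cost is two sentences and one cross-reference, by protocol amendment or safety letter, plus a dermatology consult for suspected cases below Grade 3. Scheduled visits, sample size and the efficacy analysis do not change.

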#### 5.4.4.2.2. *Criteria to Resume Treatment*

Subjects may resume treatment with AGEN2034 when drug-related AE(s) resolve(s) to Grade 1 or baseline value, with the following exceptions:

- Subjects may resume treatment in the presence of Grade 2 fatigue.
- Subjects who have not experienced a Grade 3 drug-related skin AE may resume treatment in the presence of Grade 2 skin toxicity.

- Subjects with baseline Grade 1 AST/ALT or total bilirubin who require dose delays for reasons other than a 2-Grade shift in AST/ALT or total bilirubin may resume treatment in the presence of Grade 2 AST/ALT or total bilirubin.
  - Subjects with combined Grade 2 AST/ALT AND total bilirubin values meeting discontinuation parameters ([Section 4.4.1](#)) should have treatment permanently discontinued.
- Drug-related pulmonary toxicity, diarrhea, or colitis must have resolved to baseline before treatment is resumed.
- Drug-related endocrinopathies adequately controlled with only physiologic hormone replacement may resume treatment.
- Subjects who received systemic corticosteroids for management of any drug-related toxicity must be off corticosteroids or have tapered down to an equivalent dose of prednisone  $\leq$  10 mg/day.

#### **5.4.5. Treatment Beyond Disease Progression**

Subjects will be permitted, with the Sponsor's approval, to continue with treatment beyond initial RECIST 1.1 defined progressive disease (PD) as long as they meet the following criteria:

- Investigator-assessed clinical benefit from the treatment;
- Is clinically stable (see definition in [Section 4.4.1](#));
- Subject is tolerating study drug; and
- There is agreement with the sponsor.

The assessment of clinical benefit should take into account whether the subject is clinically deteriorating and unlikely to receive further benefit from continued treatment. The following criteria need to be taken into consideration:

- Absence of clinical symptoms and signs (including worsening of laboratory values) indicating disease progression.
- No decline in ECOG performance status.
- Absence of rapid progression of disease or of progressive tumor at critical anatomical sites (e.g., cord compression) requiring urgent alternative medical intervention.

Subjects should discontinue study therapy upon evidence of further progression, defined as an additional 10% or greater increase in tumor burden from time of initial progression (including all target lesions and new measurable lesions).

Imaging is required every 6 weeks ( $\pm$  3 days) for those subjects with PD who remain on AGEN2034 until treatment is discontinued.

At the time of initial progression, new lesions are considered measurable if the longest diameter is  $\geq$  10 mm (except for pathological lymph nodes, which must have a short axis of  $\geq$  15 mm). Any new lesion considered non-measurable at the time of initial progression may become measurable and therefore included in the tumor burden measurement if the longest diameter

increases to  $\geq 10$  mm (except for pathological lymph nodes, which must have an increase in short axis to  $\geq 15$  mm).

